Subjects will receive study treatment as continuous 28-day cycles. Treatment cycles will be counted continuously regardless of dose interruptions. Subjects will undergo safety and efficacy assessments as defined in the Schedule of Procedures/Assessments and in the Schedule of Assessments after the Data Cutoff for the Primary Analysis. After the data cutoff for the primary analysis subjects, will be eligible to receive study treatment as continuous 56-day cycles.

Subjects will discontinue study treatment upon evidence of progressive disease, as judged by the Investigator. After disease progression, subjects will be followed for survival and PFS2 until data cutoff for the primary analysis.

This study will consist of 2 phases, the Prerandomization Phase, and the Randomization Phase with treatment continuing after the data cutoff for the primary analysis.

The **Prerandomization Phase** will last no longer than 28 days and will include a Screening Period to establish protocol eligibility and a Baseline Period to confirm eligibility and establish disease characteristics prior to randomization and treatment. Repeated laboratory evaluation to establish eligibility is not allowed unless discussed and agreed upon with the sponsor.

The **Randomization Phase** will consist of a Treatment Period and a Follow-up Period. It will begin at the time of randomization of the first subject and will end at the data cutoff for the primary analysis, which is defined as when all randomized subjects complete the Week-24 tumor assessments or discontinue study treatment before Week 24. Subjects will be randomly assigned to treatment in a

1:1 ratio.

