After the data cutoff for the primary analysis, the **Treatment Period** will consist of **56-day treatment cycles** and an Off-Treatment Visit, where subjects still on study treatment following the data cutoff of the planned primary analysis (ie, at the end of the Randomization Phase) will continue to receive the same treatment they received during the Randomization Phase. Study treatment will continue until confirmed disease progression, development of unacceptable toxicity, subject request, withdrawal of consent, lost to follow up or study termination by the sponsor. If the study is terminated by the sponsor, study drug (s) will be provided to subjects where commercial access is not available. Tumor assessments will be performed according to the local standard of care, and scans will no longer be required to be sent to the imaging core laboratory (ICL). The Off-Treatment Visit will occur within 28 days after the final dose of study treatment. After the data cutoff for the primary analysis, all AEs leading to study drug discontinuation and SAEs will be recorded until 28 days after the last dose of study drug.

The definition of the **End of the Study** is the last subject's last assessment (Off-Treatment Visit) after the data cutoff for the primary analysis.

The data obtained after the data cutoff for the primary analysis will be summarized and included in the CSR at the end of study as an addendum.

Number of Subjects

Approximately 338 subjects will be randomized (169 subjects in each treatment arm).

Inclusion Criteria

1. Histological or cytological confirmation of predominant clear cell RCC (original tissue diagnosis of RCC is acceptable).

2. Documented evidence of advanced RCC.
3. One prior disease progression episode on or after VEGF-targeted treatment (for example, but not limited to, sunitinib, sorafenib, pazopanib, cabozantinib, bevacizumab, axitinib, vatalanib, AV951/tivozanib) administered for the treatment of RCC. Prior PD-1/PD-L1 treatment in addition to 1 prior VEGF-targeted treatment is allowed.
4. At least 1 measurable target lesion according to RECIST 1.1 meeting the following criteria:
 - Lymph node (LN) lesion that measures at least 1 dimension as ≥ 1.5 cm in the short axis
 - Non-nodal lesion that measures ≥ 1.0 cm in the longest diameter

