The following guidelines should be followed for the management of Grade 4 hypertension (life-threatening consequences):

1. Institute appropriate medical management
2. Discontinue study treatment

MANAGEMENT OF PROTEINURIA

Regular assessment of proteinuria should be conducted as detailed in the Schedule of Procedures/Assessments. Guidelines for assessment and management of proteinuria:

1. Grading will be based on the 24-hour urinary protein result. Management of lenvatinib administration will be based on the grade of proteinuria according to the "Dose Modification Guidelines for Lenvatinib-Everolimus Combination Treatment-Related Toxicity."
2. A 24-hour urine collection (within 72 hours) to verify the grade of proteinuria for protein quantitation is required in the following situations:
 - The first (initial) occurrence of $\geq 2+$ proteinuria on urine dipstick while on study drug

- A subsequent increase in severity of urine dipstick proteinuria occurring on the same lenvatinib dose level
 - When there has been a lenvatinib dose reduction and at the new dose level the urine protein dipstick result is 2+, 3+, or 4+
3. Urine dipstick testing for subjects with proteinuria $\geq 2+$ should be performed every 2 weeks (or more frequently as clinically indicated) until the results have been 1+ or negative for 1 treatment cycle (ie, 56-day cycle).

MANAGEMENT OF DIARRHEA

An anti-diarrheal agent should be recommended to the subject at the start of study treatment and subjects should be instructed and educated to initiate anti-diarrheal treatment at the first onset of soft bowel movements. The choice of anti-diarrheal agent should be individualized to the subject's clinical circumstances and follow standard medical practice. If signs/symptoms of diarrhea persist despite optimal medical management, instructions contained in the "Dose Modification Guidelines for Lenvatinib-Everolimus Combination Treatment-Related Toxicity" should be followed.

MANAGEMENT OF NON-INFECTIOUS PNEUMONITIS

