9.4.2.2 Management of Hypertension

Hypertension is a recognized side effect of treatment with drugs inhibiting VEGF signaling. Investigators should therefore ensure that subjects enrolled to receive treatment with lenvatinib have BP of $\leq 150/90$ mmHg at the time of study entry and, if known to be hypertensive, have been on a stable dose of antihypertensive therapy for at least 1 week before Cycle 1/Day 1. Early detection and effective management of hypertension are important to minimize the need for lenvatinib dose interruptions and reductions.

Antihypertensive agents should be started as soon as elevated BP (systolic BP ≥ 140 mmHg or diastolic BP ≥ 90 mmHg) is confirmed on 2 assessments a minimum of 30 minutes apart. One BP assessment is defined as the mean value of 3 measurements at least 5 minutes apart. After the data cutoff for the primary analysis, one BP assessment is defined as the mean value of 2 measurements at least 5 minutes apart. The choice of antihypertensive treatment should be individualized to the subject's clinical circumstances and follow standard medical practice. For previously normotensive subjects, appropriate antihypertensive therapy should be started when systolic BP ≥ 140 mmHg or diastolic BP ≥ 90 mmHg is first observed on 2 assessments a minimum of 30 minutes apart. For those subjects already on antihypertensive medication, treatment modification may be necessary if hypertension persists.

Lenvatinib should be withheld in any instance where a subject is at imminent risk to develop a hypertensive crisis or has significant risk factors for severe complications of uncontrolled hypertension (eg, BP $\geq 160/100$ mmHg, significant risk factors for cardiac disease, intracerebral hemorrhage, or other significant co-morbidities). Once the subject has been on the same hypertensive medications for at least 48 hours and the BP is controlled, lenvatinib should be resumed as described below.

During the Treatment Period, subjects with systolic BP ≥ 160 mmHg or diastolic BP ≥ 100 mmHg must have their BP monitored on Day 15 or more frequently as clinically indicated until systolic BP has been ≤ 150 mmHg and diastolic BP has been ≤ 95 mmHg for 1 treatment cycle (ie, 56-day cycle). If a repeat event of systolic BP ≥ 160 mmHg or diastolic BP ≥ 100 mmHg occurs, the subject must resume the Day-15 evaluation until systolic BP has been ≤ 150 mmHg and diastolic BP has been ≤ 95 mmHg for 1 treatment cycle (ie, 56-day cycle).

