9.4.2.3 Management of Proteinuria

Regular assessment of proteinuria should be conducted as detailed in the Schedule of Procedures/Assessments (Table 6) and the Schedule of Assessments After the Data Cutoff for the Primary Analysis (Table 7). Guidelines for assessment and management of proteinuria:

1. Grading will be based on the 24-hour urinary protein result. Management of lenvatinib administration will be based on the grade of proteinuria according to instructions contained in Table 2, "Dose Modification Guidelines for Lenvatinib-Everolimus Combination Treatment-Related Toxicity,"
2. A 24-hour urine collection (within 72 hours) to verify the grade of proteinuria for protein quantitation is required in the following situations:
 - The first (initial) occurrence of $\geq 2+$ proteinuria on urine dipstick while on study drug

- A subsequent increase in severity of urine dipstick proteinuria occurring on the same lenvatinib dose level
 - When there has been a lenvatinib dose reduction and at the new dose level the urine protein dipstick result is 2+, 3+, or 4+
3. Urine dipstick testing for subjects with proteinuria $\geq 2+$ should be performed every 2 weeks (or more frequently as clinically indicated) until the results have been 1+ or negative for 1 treatment cycle (ie, 56-day cycle).

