9.5.1.4.4 VITAL SIGNS AND WEIGHT MEASUREMENTS

Vital sign measurements (ie, systolic and diastolic BP [mmHg], pulse [beats per minute], respiratory rate [per minute], body temperature [in centigrade]), and weight (kg) will be obtained at the visits designated in the Schedule of Procedures/Assessments ([Table 6](#)) by a validated method. Blood pressure and pulse will be measured after the subject has been resting for 5 minutes. All BP measurements should be performed on the same arm, preferably by the same person. One BP assessment is defined as the mean value of 3 measurements at least 5 minutes apart. After the data cutoff for the primary analysis, one BP assessment is defined as the mean value of 2 measurements at least 5 minutes apart.

Vital sign measurements (resting BP [including date and time of measurement], HR, RR and body temperature) will be obtained, excluding weight at the visits designated in the Schedule of Assessments After the Data Cutoff for the Primary Analysis ([Table 7](#)).

For subjects with an elevated BP (systolic BP ≥ 140 mm Hg or diastolic BP ≥ 90 mmHg), confirmation should be obtained by performing 2 assessments a minimum of 30 minutes apart.

Subjects with systolic BP ≥ 160 mmHg or diastolic BP ≥ 100 mmHg must have their BP monitored every 2 weeks (on Day 1 and Day 15 or more frequently, as clinically indicated) until systolic BP has been ≤ 150 mmHg and diastolic BP has been ≤ 95 mmHg for 1 treatment cycle (ie, 56-day cycle). A diary will be provided to the subject to capture the BP evaluations between study visits. See subsection for management of hypertensive subjects ([Section 9.4.2.2](#)).

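### After the data cutoff, the named blood-pressure check days (Day 1 and Day 15) no longer deliver the stated two-weekly interval, because the cycle is 56 days

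*Protocol*

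**What the plan says.** **Cycle length.** The synopsis states that after the data cutoff subjects may receive "study treatment as continuous 56-day cycles". Section 9.4.6 says the same and keeps 28 days for the Randomization Phase. The cutoff falls "when all randomized subjects complete the Week-24 tumor assessments or discontinue study treatment before Week 24".

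**Blood pressure at or above 160 systolic or 100 diastolic.** Three places set the monitoring rule:

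- Protocol 9.5.1.4.4 requires checks "every 2 weeks (on Day 1 and Day 15 or more frequently, as clinically indicated"), until pressure has been controlled for one 56-day cycle.
- Protocol 9.4.2.2 says that the same subjects "must have their BP monitored on Day 15 or more frequently as clinically indicated", until controlled at the stated "mmHg for 1 treatment cycle (ie, 56-day cycle"). It gives no two-weekly interval. For a repeat event it again refers only to the Day-15 evaluation.
- The synopsis section on hypertension repeats the 9.4.2.2 wording.

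Table 7, the post-cutoff schedule, marks vital signs for the treatment-period visits. Its footnote b provides a diary for readings between visits and refers sites to the hypertension-management text. The footnote gives no interval.

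**Proteinuria, for comparison.** Section 9.4.2.3 says that dipstick testing "should be performed every 2 weeks (or more frequently as clinically indicated") and names no days. Table 7 footnote h points to that section.

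**Liver tests.** Section 9.4.2.8 asks for ALT, AST and bilirubin every two weeks for two months and monthly after that, and cites both Table 6 and Table 7. Table 7 has 8-week cycles, and its footnote g ties chemistry review to dosing in each cycle. Section 9.5.1.4.3 places post-cutoff laboratory work within 72 hours of Day 1.

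**The concern.** The interval and the named days in 9.5.1.4.4 agree in a 28-day cycle. The sentence already refers to a 56-day cycle, yet its day numbers were not extended to match. The other two statements of the rule give only Day 15, so the two-weekly minimum appears in one place, and Table 7 does not send sites there.

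At stake is consistent monitoring of subjects with marked hypertension who stay on lenvatinib plus everolimus after the cutoff. Under 9.4.2.2 these readings decide whether antihypertensives are started or increased and whether lenvatinib is interrupted and restarted at a lower dose. A site that follows Table 7 to 9.4.2.2 could fall short of the protocol's own minimum without noticing.

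The liver-test point is of the same kind but lesser weight: a section requires one frequency and cites a table that schedules another.

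**Working it through.** **Inputs.** Named blood-pressure days: 1 and 15 (9.5.1.4.4). Stated interval: 2 weeks = 14 days (9.5.1.4.4). Cycle length: 28 days before the cutoff and 56 days after it (9.4.6). Visit window: ±3 days (Table 7 footnote a). Assumption: the once-per-cycle visit in Table 7 falls on Day 1, as 9.5.1.4.3 implies for laboratory work.

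**Step 1: reproduce the stated interval.** The gaps are (Day 15 − Day 1) and (next Day 1 − Day 15), where the next Day 1 is Day 1 + cycle length.

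| Cycle | First gap | Second gap | Two-weekly? |
|---|---|---|---|
| 28 days | 15 − 1 = 14 | 29 − 15 = 14 | yes |
| 56 days | 15 − 1 = 14 | 57 − 15 = 42 | no |

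The long gap is 42/14 = 3 times the stated interval. If each visit may move by 3 days, it runs from 42 − 6 = 36 to 42 + 6 = 48 days.

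**Step 2: count the checks.** A two-weekly rule needs 56/14 = 4 checks per cycle (Days 1, 15, 29 and 43). The named days supply 2.

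**Step 3: the release rule on each reading.** Control over one 56-day cycle, counting both ends, rests on Days 1, 15 and 57 (3 readings) if only the named days are used. It rests on Days 1, 15, 29, 43 and 57 (5 readings) if the two-weekly interval is kept.

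**Step 4: 9.4.2.2 and the synopsis.** These name Day 15 only. With the cycle visit on Day 1, the pattern is again 14 and 42 days, and here there is no interval in the text to correct it.

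**Step 5: proposed days.** Days 1, 15, 29 and 43 of a 56-day cycle give gaps of 14, 14, 14 and 14 days.

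**Step 6: liver tests.** Any subject still on treatment at the cutoff has passed Week 24 (24 × 7 = 168 days), well beyond two months (about 61 days), so the monthly rule is the one that applies. One panel per 28-day cycle gives 365.25/28 = 13.0 a year, which satisfies it. One panel per 56-day cycle gives 365.25/56 = 6.5 a year, against 12 for monthly. A second panel on Day 29 gives gaps of 28 and 28 days.

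**The case against.** The strongest reply is that 9.5.1.4.4 makes two-weekly monitoring mandatory and allows more frequent checks, so a site that obeys the whole sentence measures on Days 1, 15, 29 and 43. That stands. A reader might infer that the protocol prescribes a 42-day gap; it does not. The gap arises only for a site that works from the named days, or from 9.4.2.2 or the synopsis, where the interval is absent.

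It can also be said that the stricter text satisfies all three, that 9.4.2.2 requires treatment and, if pressure stays high despite maximal therapy, interruption, and that a diary is supplied. These soften the point. They do not remove it: allowing checks when clinically indicated sets no minimum, and the diary has no stated frequency. Diary readings become a sufficient answer once dates are attached to them.

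On liver tests, footnote g does not cap testing at once per cycle, so a site can meet both texts. Footnote g lacks the pointer to the management section that footnote h has for proteinuria. A reader might infer that about 5.5 fewer panels a year (12 − 6.5) is a safety deficit. The documents do not show that 8-weekly testing is harmful at this stage, and lighter monitoring may have been intended. Nor does 9.5.1.4 help that reading: it ties chemistry to drug administration and clinical need and states no 8-week interval.

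A reader might also infer that the 56-day control requirement shortens the three consecutive months in Table 6. Table 6 is headed for the Randomization Phase with 28-day cycles, so the two most naturally apply to different periods, and no shortfall follows.

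**Conclusion.** The point holds as a minor safety-conduct correction. After the cutoff, the named blood-pressure days cover 2 of the 4 two-weekly checks in a cycle and leave up to 42 days between scheduled checks against the stated 14 (36 to 48 with the visit window). This rests on a site using the named days, and on the Table 7 cycle visit falling on Day 1.

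The liver-test mismatch is a secondary harmonisation: monthly in 9.4.2.8 against once per 8 weeks in the table it cites.

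Nothing here bears on the primary endpoints. Both are defined over the first 24 weeks after randomization, and 56-day cycles begin only after every randomized subject has completed the Week-24 tumor assessments or stopped treatment. No sample-size, power or error-rate figure is involved.

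**What to change.** **Blood pressure.** In 9.5.1.4.4, 9.4.2.2 and the synopsis, state the same rule for subjects at or above 160 systolic or 100 diastolic: every 2 weeks (Days 1, 15, 29 and 43 of a 56-day cycle; local check or diary reading allowed). The 28-day schedule in Table 6 needs no change.

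**Liver tests.** Choose one: add a Day 29 local liver panel to Table 7, or limit the monthly requirement in 9.4.2.8 to the Randomization Phase so that Table 7 governs afterwards. The choice is the sponsor's.

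**Cost.** Protocol wording, or a clarification letter to sites. At most two extra blood-pressure readings per 56-day cycle for affected subjects, and none at sites already keeping the two-weekly interval. One extra local liver panel per cycle only if monthly testing is kept.

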9.5.1.4.5 PHYSICAL EXAMINATIONS

Physical examinations will be performed as designated in the Schedule of Procedures/Assessments ([Table 6](#)) and in the Schedule of Assessments After the Data Cutoff for the Primary Analysis ([Table 7](#)). Documentation of the physical examination will be included in the source documentation at the site. Only changes from screening physical examination findings that meet the definition of an AE will be recorded on the Adverse Events CRF. A symptom-directed physical examination will be performed as clinically indicated.

9.5.1.4.6 ELECTROCARDIOGRAMS

ECGs will be performed during screening and every 4 weeks on Day 1 of each cycle during the Randomization Phase beginning with Cycle 2 and at the Off-Treatment Visit ([Table 6](#)). After the data cutoff for the primary analysis, ECGs may be performed as clinically indicated ([Table 7](#)). Complete, standardized, 12-lead ECG recordings that permit all 12 leads to be displayed on a single page with an accompanying lead II rhythm strip below the customary 3 \times 4 lead format are to be used. In addition to a rhythm strip, a minimum of 3 full complexes should be recorded from each lead simultaneously. Subjects are suggested to be in the recumbent position for a period of 5 minutes prior to the ECG.

An ECG abnormality may meet the criteria of an AE as described in this protocol (see [Section 9.5.1.4.1](#)) and the CRF Completion Guidelines. In these instances, the AE corresponding to the ECG abnormality will be recorded on the Adverse Events CRF.

9.5.1.4.7 ECHOCARDIOGRAM OR MULTIPLE GATED ACQUISITION SCAN

A MUGA scan (using technetium-^{99m}-pertechnetate) or an echocardiogram to assess LVEF will be performed at Screening and as clinically indicated ([Table 6](#)) and ([Table 7](#)). MUGA or echocardiogram scans should be performed locally in accordance with the institution's standard practice. MUGA scans are the preferred modality; however, whichever modality is used for an individual subject at Baseline should be repeated for all subsequent LVEF assessments for that subject. LVEFs as assessed by the institution will be entered onto the CRF. Investigator assessment will be based upon institutional reports.

9.5.1.4.8 PREGNANCY TEST

A serum or urine pregnancy test (β -hCG or hCG with a minimum sensitivity of 25 IU/L or equivalent units of β -hCG or hCG) will be performed in women of childbearing potential (ie, premenopausal women and postmenopausal women who have been amenorrheic for less than

12 months). Samples of blood or urine will be taken at designated time points as specified in the Schedule of Procedures and Assessments (Table 6) and Schedule of Assessments After the Data Cutoff for the Primary Analysis (Table 7).

9.5.1.5 Other Assessments

HRQoL will be assessed at Baseline (prior to first dose of study drug), on Day 1 of each subsequent cycle, and at the Off-Treatment Visit in the Randomization Phase. HRQoL will not be assessed after the data cutoff for the primary analysis. Every effort should be made to administer HRQoL surveys prior to study drug administration and before other assessments and procedures. Subjects will complete the Cancer Therapy-Kidney Symptom Index-Disease Related Symptoms (FKSI-DRS; Appendix 9), the European Organization for the Research and Treatment of Cancer (EORTC) QLQ-C30 (Appendix 10) and the European Quality of Life (EuroQol) EQ-5D-3L (Appendix 11) instruments.

The FKSI-DRS consists of 9 items that experts and patients have indicated are important targets for the treatment of advanced kidney cancer, and that clinical experts have indicated are primarily disease-related, as opposed to treatment-related. Symptoms assessed on the FKSI-DRS include pain, fatigue, shortness of breath, fevers, weight loss, coughing, and blood in urine. The total score can range from 0 (worst) to 36 (best).

The QLQ-C30 measure comprises 9 multiple-item scales and 6 single items. Multiple-item scales of QLQ-C30 consist of 6 functional scales (physical, role, emotional, cognitive, social and global QoL) and 3 symptom scales (fatigue, nausea and vomiting, pain). Six single-item scales of QLQ-C30 involve dyspnea, sleep disturbance, appetite loss, constipation, diarrhea and financial impact. All of the derived scales range in score from 0 to 100. For the overall HRQoL and functioning scales, a higher score is correlated with better HRQoL, whereas a higher score represents worse HRQoL for symptom scales.

The EQ-5D-3L generic QoL questionnaire is comprised of 5 dimensions: mobility, self-care, usual activities, pain or discomfort, and anxiety or depression. Each dimension has 3 levels (1) no problem, (2) some problem, or (3) extreme problem. Thus, the final scoring consists of 243 possible combinations or health states. The utility value for each state is assigned on the basis of a set of preference weights (tariffs) elicited from the general population.

